##### **3.1.2 Primary Objectives**

To determine if the DETOURS opt-out protocol for antibiotic de-escalation will lead to reduction in antibiotic use among eligible patients identified with suspected sepsis.

##### **3.1.3 Secondary Objectives**

To determine if the DETOURS opt-out protocol for antibiotic de-escalation will lead to improvement in DOOR among eligible patients identified with suspected sepsis.

To determine if the DETOURS opt-out protocol for antibiotic de-escalation will lead to reduction in *C. difficile* infections among eligible patients identified with suspected sepsis.

To determine if the DETOURS opt-out protocol for antibiotic de-escalation will lead to change in patient outcomes among eligible patients identified with suspected sepsis, including in-hospital mortality, length of stay, and subsequent ICU transfer compared to eligible patients in control units.

## 4 STUDY DESIGN

The DETOURS study will be a prospective, multicenter randomized controlled trial. The active component of the quality improvement study will be performed over approximately 2 years, from April 2018 through February 2020.

### 4.1 Study Population

#### 4.1.1 Selection of the Study Population

Subjects will be recruited from hospitals participating in either the CDC Prevention Epicenters Program or the Duke Antimicrobial Stewardship Outreach Network (DASON) (**Appendix 1**). The CDC Prevention Epicenters Program is a government-funded, 4-year grant that allows for collaboration on several projects dealing with infection diseases in healthcare. From the Epicenters Program, Washington University in St. Louis and the University of Pennsylvania will be collaborating with Duke University on this project. DASON is a network of 29 community hospitals in the United States designed to improve outcomes for patients and hospitals by optimizing antimicrobial use.

#### 4.1.2 Inclusion/Exclusion Criteria

**Inclusion criteria:** All acute care, adult, non-ICU patients with suspected sepsis are potentially eligible for intervention if they meet the following criteria:

1. Blood culture preliminary results that indicate no growth as of 48-96 hours.
  - a. Exception: Patients with a single positive blood culture for coagulase negative Staphylococcus and no central line in place will also be included.

**AND**

2. Still on broad spectrum antibiotic therapy after 48-96 hours.
  - a. Broad spectrum antibiotics will be defined by agent as described in the rank list below (Table 1). Any agent in the 2, 3, or 4 rank categories will be considered broad spectrum.

**Table 1. Spectrum rank categories for commonly used antimicrobial agents.**

Narrow spectrum	Broad spectrum	Extended spectrum, including MDRO and Pseudomonas	Protected
1	2	3	4
1st- and 2nd-generation cephalosporins Amoxicillin TMP/SMX Nafcillin, Oxacillin Metronidazole Doxycycline Nitrofurantoin Penicillin	Ceftriaxone 3rd-generation oral cephalosporins Azithromycin Clarithromycin Amoxicillin/clavulanate Ampicillin/sulbactam Clindamycin	Anti-pseudomonal penicillins Fluoroquinolones Aminoglycosides Vancomycin Cefepime, Ceftazidime Ertapenem Aztreonam	Anti-pseudomonal Carbapenem Colistin Tigecycline Linezolid, Tedizolid Daptomycin Ceftaroline Ceftazidime/avibactam Ceftolozane/tazobactam

**Exclusion criteria:** Adult patients who are located in ICU wards will not be eligible for enrollment.

Any patient meeting eligibility criteria described above will be included without regard to adult age, gender, race, insurer status, or other discriminating variables. Patients will be enrolled only once, even if they meet eligibility criteria a second time within the study period.

### 4.1.3 Treatment Assignment Procedures

Individual patients will be randomized to intervention or control (1:1). Participating sites will be provided site-specific randomization schema to ensure adequate representation of each arm within individual study sites.

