**Randomization**

Subjects who pass the Safety Checklist will be randomized to intervention (the Opt-Out Procedure) or control (standard care, no interaction with study team). Each study site will be provided with a randomization scheme.

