### ***Blinding***

Study personnel and pharmacists will remain blinded to randomization status until Step 3 of the Opt-Out Procedure. In other words, the determination for eligibility and application of the Safety Check will occur prior to knowledge of randomization. No further blinding of study personnel will occur as this is an active, quality-improvement activity that utilizes front-line clinical personnel. No contact with individual patients is anticipated.

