## 9.2 Randomization

Randomization will be performed using capabilities of the web-based RedCap system. Eligible patients will be randomized in a 1:1 ratio to intervention versus standard of care, with randomization stratified by hospital. Randomization scheme will be generated by the study statistician.

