**Step 1**

# 1 Screening

Goal Identify the pool of patients potentially eligible for the intervention

- Blood cultures negative at 48-72 hours\*  
\* OK to include CoNS patients without a central line
- Patient on broad-spectrum antibiotics  
(Rank 2, 3 or 4 on Antibiotic Rank Chart)

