**Step 3**

# 3 Randomization

Goal | Determine if patient is randomized to intervention or standard of care

Consult Randomization Scheme provided by study team

Is the patient randomized to intervention?

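### The protocol describes allocation in two ways, a scheme given to sites and randomization in REDCap, and does not say how the arm is withheld until the Safety Check is recorded

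*Protocol*

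**What the plan says.** Three places in the protocol put a randomization scheme in the hands of sites:

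- Section 4.1.3: "Participating sites will be provided site-specific randomization schema to ensure adequate representation of each arm within individual study sites".
- Section 4.1.4, Randomization: "Each study site will be provided with a randomization scheme".
- Appendix 2, Step 3, part of the material issued to every site: "Consult Randomization Scheme provided by study team". This card does not mention REDCap.

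Section 9.2 describes a central mechanism: "Randomization will be performed using capabilities of the web-based RedCap system". It adds 1:1 allocation stratified by hospital, and "Randomization scheme will be generated by the study statistician".

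The Blinding paragraph of Section 5.1 gives the intended order: "Study personnel and pharmacists will remain blinded to randomization status until Step 3 of the Opt-Out Procedure", and "the determination for eligibility and application of the Safety Check will occur prior to knowledge of randomization".

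Under Section 4.1.4, meeting any one Safety Check item keeps a patient out of randomization. Section 5.1 has the checklist result and the reasons for failure entered in REDCap.

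On a separate matter, the Appendix 2 Step 1 card reads "Blood cultures negative at 48-72 hours". The synopsis and Sections 4.1.2 and 4.1.4 use 48-96 hours, and the version history records a change to 48-96 hours at version 3.0.

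**The concern.** The Safety Check is the gate to randomization, and site staff apply it. Some items are objective, such as pregnancy, transplant or a CD4 count below 200. Others, such as significant leukocytosis or ongoing respiratory insufficiency, carry no threshold in the text available. If whoever applies the check can see the next allocation, a borderline patient can be passed or failed according to the arm that is waiting. The arms would then differ before treatment starts.

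The primary outcome is days of therapy (DOT), and expected course length is something a pharmacist may well be able to judge at screening. Section 9.4.1 fits treatment as the only covariate, so the primary model would not correct such an imbalance. Staff are unblinded after Step 3, so concealment up to that step is the only protection of this kind.

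**Working it through.** **1. The passages side by side**

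| Place | Who has the scheme | How the arm is withheld |
|---|---|---|
| 4.1.3 | provided to the site | not stated |
| 4.1.4, Randomization | provided to the site | not stated |
| Appendix 2, Step 3 | staff consult it | not stated |
| 9.2 | generated by the statistician, run in REDCap | not stated |
| 5.1, Blinding | not addressed | order asserted, no mechanism |

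Under Section 9.2 the stated order is secured only if REDCap withholds the arm until the Safety Check is entered. Under the other three places it is unprotected if the scheme is a readable list.

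**2. How long a visible slot would stay visible.** Table 4 expects 2 patients a month at each community hospital, so the next slot would stand open for about half a month (1/2 month). At 10 a month in the academic hospitals it would stand open for about a tenth of a month.

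**3. What would be audited.** Section 15 re-checks the Safety Check in 15-20% of enrolled patients, and Appendix 4 in all enrolled patients. Neither covers patients who failed it.

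**4. The plan's own figures.**
- Sample size: 150 + 180 + 180 + 7 x 36 = 762, as stated.
- Power for a 25% reduction, by simulation from the protocol's model (control mean 11.4, dispersion 1.68, hospital variance 0.12, 10 hospitals, two-sided 0.05 assumed): 87.2%, against 87% stated.
- Wald cross-check with 381 per arm: SE = sqrt[(1/11.4 + 1.68)/381 + (1/8.55 + 1.68)/381] = 0.0967; |log 0.75|/SE = 0.2877/0.0967 = 2.97; power = Phi(2.97 - 1.96), about 84.5%.

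The concern changes neither figure.

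**5. Size of a spurious shift (assumed inputs).** Let p be the share of long-course patients, r their mean DOT relative to the rest, and f the fraction of them failed when the next slot is intervention. With no treatment effect,

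shift = 1 - [(1 - p) + p(1 - f)r] / [(1 - pf)(1 + p(r - 1))].

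| p | r | f | Calculation | Shift |
|---|---|---|---|---|
| 0.10 | 1.5 | 0.25 | 1 - 1.0125/(0.975 x 1.05) | 1.1% |
| 0.20 | 2 | 0.25 | 1 - 1.10/(0.95 x 1.2) | 3.5% |
| 0.20 | 2 | 0.50 | 1 - 1.00/(0.90 x 1.2) | 7.4% |
| 0.20 | 2 | 1 | 1 - 0.80/(0.80 x 1.2) | 16.7% |
| 0.30 | 3 | 1 | 1 - 0.70/(0.70 x 1.6) | 37.5% |

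The protocol gives no value for p, r or f.

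**6. What a shift would do to the test.** If selection alone lowered mean DOT by 10%, with the spread unchanged, the trial would declare an effect as often as its power at 10%. That is 28% in the Section 9.1 table, 31.6% in the simulation and 19.3% by Wald. For a 5% shift the figures are 15.1% (simulation) and 7.7% (Wald). The simulated analysis already rejected 11.4% of the time with no effect, because the robust standard error rests on only 10 hospitals. The simulation figures should be read against that level. Some fits reached the iteration limit, so small differences mean little.

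**The case against.** The strongest reply is that the passages can be reconciled. Section 9.2 itself speaks of a scheme made by the statistician next to the sentence on REDCap. A site-specific scheme loaded in REDCap and opened at Step 3 would fit every passage, including the Blinding paragraph. This stands. A reader might infer that sites do know the next arm, or that the stated blinding is impossible. The documents do not support that: none of them says the scheme is an open list.

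Four further points limit the concern.

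- **Judgement in the checklist.** A reader might take the whole check to be subjective. Several items are objective. Section 4.1.4 refers to Appendix 2 for further definitions, and figures there are not shown, so thresholds may exist.
- **Motive.** Section 4.1.4 plans feedback every 4 weeks and, ideally, comparison between units. The feedback concerns protocol compliance, not DOT, so it does not plainly reward failing long-course patients. Nor does the protocol fix that the same person screens and intervenes. Any motive is inferred.
- **Records.** Safety Check results and failure reasons are captured for all eligible patients, and exclusions are a process indicator. Unusual patterns of failure could be looked for. This allows detection, not prevention, and the failures themselves are not verified.
- **Magnitude.** No single figure for the bias can be defended, because every input is assumed.

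What the reply does not supply is any sentence that makes REDCap withhold the arm, or that keeps the list away from sites. The card that staff work from points to a scheme and not to REDCap.

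**Conclusion.** The concern holds as an unresolved inconsistency about allocation concealment. The protocol intends that the Safety Check comes before knowledge of the arm, but describes the mechanism in two ways and secures the order in neither. It does not follow that concealment has failed or that selection has occurred.

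The possible bias in mean DOT is unknown. Under assumed long-course shares of 10-30%, DOT ratios of 1.5-3, and a quarter to all of such patients failed ahead of an intervention slot, it ranges from about 1% to 38%, against a design effect of 25%. Sample size and power are unaffected.

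The screening window is a separate and smaller matter. It applies before randomization and equally to both arms, so it affects who is screened and not the fairness of allocation. A reader might infer that sites are dropping patients at 72-96 hours; the documents show only that the card and the protocol body disagree.

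**What to change.** 1. Reword Section 4.1.3, the Randomization paragraph of Section 4.1.4 and the Appendix 2 Step 3 card to agree with Section 9.2: allocation is obtained from REDCap.
2. State once, preferably in Section 9.2, that no site holds the list and that REDCap releases the arm only after the Safety Check result has been saved.
3. Separately, reconcile the Appendix 2 Step 1 window with Section 4.1.2 and the version 3.0 change when the cards are reissued.

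The cost is wording in a few places and a reissued card. REDCap is already planned for randomization and already captures the Safety Check result.

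Two inexpensive additions would help. The quality control in Section 15 and Appendix 4 could include a sample of Safety Check failures. Because Section 9.1 shows that version 4 was written after the study began, the study team should also document how arms were issued to patients already randomized, since new wording cannot protect those allocations.

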### 4.1.4 Stewardship Strategy Descriptions

#### General principles

[figure not shown]
Initial management of patients with suspected sepsis will occur according to local site practices. That is, the study protocol will not direct site physician practice regarding the use of specific antibiotics.

Our intervention represents the operationalization of a combined strategy of routine reassessment of patients with suspected sepsis and consideration for discontinuation of antibiotics or narrowing the spectrum and/or number of antibiotics. The intervention has been vetted through the DETOURS expert panel as described in Section 2 “Risks.” Eligible patients will begin the protocol by default (ie, a patient-specific order will not be required). Each study site will implement the opt-out protocol in the method that best fits their local preferences, clinical work flow, and personnel. Personnel performing assessments of inclusion criteria and interacting directly with providers may vary slightly depending on local resources and strategy. In general, the opt-out protocol is designed for use by clinical pharmacists or centralized antibiotic stewardship pharmacists in interacting with primary providers (e.g. physicians, mid-level providers). This process will be modeled after the communication mechanism for pharmacy-led IV-to-PO conversion policies at each site.

#### OPT-OUT PROTOCOL

Eligible patients will be selected from the pool of patients receiving antibiotic therapy (Figure 1). The **Opt-out Protocol** includes five steps (numbers 1-5 in Figure 1). Additional documents summarizing these steps are provided in Appendix 2. Eligible patients must pass each sequential step to proceed to the next step:

Figure 1. Enrollment flow chart

1. Eligibility screen
2. Safety Check
3. Randomization
4. Opt-Out Procedure
5. Guided De-escalation Discussion

Designated personnel will screen patients at study sites on a daily basis, if possible, and on weekdays with catch-up procedures on Mondays only if necessary due to personnel constraints.

**Eligibility Screen**

First, a unit census list, list of preliminary blood culture results, and active antibiotic orders will be screened to apply the inclusion criteria. Patients meeting initial inclusion criteria (negative blood culture results at 48-96 hours and broad-spectrum antibiotics), will then undergo the Safety Check.

**Safety Checklist**

The Opt-Out Protocol was designed to ensure patient safety. Thus, all eligible patients go through a safety check prior to implementation of the Opt-Out Procedure (Table 2). Appendix 2 provides additional definitions and instructions for the Checklist components. Patients meeting any one of the checklist criteria will be considered “high risk” and will be excluded from the Opt-out Procedure; antibiotics will be continued per standard care processes. However, if none of the Safety Screen Checklist criteria are met, the subject will undergo randomization.

*Table 2. Safety Screen Checklist*

**Safety Check** Patient fails if meets one or more of the following criteria

1. Ongoing Signs/ Symptoms of Infection          continued fever          new chest x-ray infiltrate          empyema          lung abscess          continued significant leukocytosis
 
2. Concerning/Inadequate Microbiological Data          positive blood cultures*          *Note: OK to stop if contaminant and no central line          positive microbiological data          no cultures during sepsis work-up          antibiotic use prior to blood culture
	
3. High-Risk Comorbidity/Severe Illness          bronchiectasis          asplenia/splenectomy          cystic fibrosis          pregnant          recent I&D procedure          ongoing respiratory insufficiency          immunocompromised          HIV/AIDS with CD4 count < 200          taking immunosuppressive agents          agammaglobulinemia          bone marrow aplasia          neutropenia          transplant recipient

--	---

**Randomization**

Subjects who pass the Safety Checklist will be randomized to intervention (the Opt-Out Procedure) or control (standard care, no interaction with study team). Each study site will be provided with a randomization scheme.

**Opt-out Procedure**

The assessor will approach the primary provider in charge of antibiotic decision-making either one-on-one in person, on team rounds, or by phone/pager contact as per local preference. The assessor will inform the provider:

“[This patient] has passed the initial safety screen for de-escalation of antibiotics. Antibiotics will be stopped per protocol unless you opt-out.”

If the provider or clinical team agrees to stop antibiotics, then orders will be changed to reflect this decision.

### **Guided De-escalation Discussion**

If the provider or clinical team opts out and elects to continue antibiotics, the assessor will proceed with a series of the questions and dialogue that captures the provider’s rationale for continuing antibiotics, promotes and references local empiric therapy guidelines and the antibiotic rank chart (Table 1 above), encourages use of microbiology data to narrow antibiotics, and suggests clinical reassessment (guided discussion questions listed in Appendix 2, Step 5).

## **PROPOSED IMPLEMENTATION STRATEGY**

Implementation of the proposed opt-out protocol will require a multi-disciplinary team, local champions, and data feedback and response. The Engage, Educate, Execute, and Evaluate method for Quality Improvement will be used as the model for implementation. The following is a general overview of the proposed implementation strategy.

### **Leadership**

- A. Advisory Group – CDC Prevention Epicenter Programs and DASON Liaisons
- B. Local Champion(s) on each enrolled unit
  - a. Physician champion
  - b. Pharmacist champion
- C. Site Leader – TBD by each hospital
- D. Data Collection and Feedback Leader

**Engage--** All leaders will discuss the importance of 1) judicious antibiotic use and improving outcomes for patients with suspected sepsis and 2) the need for better methods for antibiotic reassessment including de-escalation and appropriate durations. Site Champions and Epicenter personnel should identify allies within each unit that can fill the Leadership roles described above. Local leaders will need to identify potential barriers to implementation while education is occurring to optimize protocol adherence.

In addition, CDC’s involvement will provide additional validity to the project and will ensure participating personnel know they are involved in an important, large quality improvement project with both local and national implications. As such, Epicenter/CDC personnel will need to discuss the overall purpose of the project with local personnel, including issues related to definitions for sepsis, de-escalation, strategy, and integrating study activities into daily routines and existing antibiotic stewardship program goals.

**Educate** – Education will begin with a “kick-off” interactive discussion with study site personnel and champions, likely performed via live webinar. This webinar would include discussion of the following:

- A. Rationale for de-escalation and the opt-out protocol
- B. Sepsis core measure and local approaches to improve sepsis care

- C. Methods used to create opt-out protocol
- D. Questions and Answers

All leaders will discuss opt-out protocol and best methods for implementation. Local champions and national experts will then discuss opt-out protocol with local unit personnel (with aid of members of the Advisory Group, as needed). Local champions will need to vet intervention with local staff. Ideally, webinar(s) could be repeated at least once to increase the number of participants. Similarly, the webinar(s) would be recorded for people who were unable to attend the live webinar session(s).

We will create binders containing opt-out protocol details and educational materials for use at each site. Additional educational materials will be created and provided throughout the study, including posters, handouts, laminated protocol cards, bibliography of relevant literature, and powerpoint presentations. Local champions will be encouraged to use these materials to conduct their own educational activities. These materials can be disseminated to local units, though each individual Epicenter will need to determine a way to produce, pay for, and disseminate the materials.

Biweekly calls will be offered to personnel to share challenges and successes and to get input from the Advisory Committee.

Finally, there may be value in having a mid-intervention “back to basics” webinar, during which much of the initial educational materials are reiterated. In addition, this would be an opportunity to address on-going questions/issues and provide broader feedback (ie, performance of the group).

**Execute** – Following the education blitz described above, each study site will implement the opt-out protocol. The standardized opt-out protocol will be provided to each site in the form of laminated cards, as costs allow. As described in the “Evaluate” section, data feedback will lead to opportunities to improve adherence to the protocol by identifying correctable defects.

Individual sites will need to determine some of the details of the implementation based on local preferences and hospital dynamics:

- A. Specifics of the opt-out protocol
- B. Personnel identified to perform the initial eligibility screen and safety checklist
- C. Preferences for communication to primary providers: timing, method, and location for opt-out procedure and de-escalation discussions
- D. Personnel responsible for documenting interventions and outcomes of the discussions

Study sites that make changes to the protocol based on the above will need to provide these changes to the central study team.

**Evaluate** – We will provide site-specific data feedback on protocol compliance to individual study site leaders (Unit Champion and Point Project Lead) every 4 weeks. Study leaders would be responsible for disseminating information to the unit staff. RAs (or other leadership personnel) can help with creation of posters and/or handouts to provide progress updates. Leadership and local personnel will identify and respond to issues identified (ie, lack of adherence or participation), with support from the Advisory Committee. Ideally, site-specific data will be contrasted with de-identified data from the other participating units to generate inter-unit competition.

